9.7 Screen failures

Screen failures are defined as subjects who consent to participate in the clinical study but do not fulfil all eligibility criteria and are not subsequently randomized in the study. A minimal set of screen failure information is required to ensure transparent reporting of screen failure subjects. Minimal information includes documentation of signed and dated informed consent form (ICF), demographics, and reason(s) for screening failure.

Subjects who do not meet the criteria for participation in this study may be rescreened.

Re-screening can be performed once if any of the following were reasons for screening failure or non-randomization (as judged by the Investigator):

- Practical reasons.
- Non-significant medical conditions (e.g. influenza, nasopharyngitis).

For subjects who are re-screened, a new screening number will be assigned and a new, signed ICF will be collected.

9.8 Subject withdrawal

9.8.1 *General withdrawal criteria*

Subjects are free to discontinue their participation in the study at any time and for whatever reason without affecting their right to an appropriate follow-up investigation or their future care. If possible, the reason for withdrawal of consent should be documented.

Subjects may be discontinued from the study at any time at the discretion of the Investigator.

Reasons for discontinuation include:

- Subject decision
- Severe non-compliance to study protocol procedures, as judged by the Investigator and/or Sponsor
- Subject is lost to follow-up.
- Significant AEs posing a risk for the subject, as judged by the Investigator and/or Sponsor
- Pregnancy
- Death

9.8.2 *Procedures for discontinuation of a subject from the study*

A subject who prematurely discontinues participation in the study will always be asked about the reason(s) for discontinuation and the presence of any AEs. If a subject withdraws consent, the Investigator must ask the subject if he/she is willing, as soon as possible, to be assessed according to the procedures scheduled for the end-of-study visit. Any ongoing AEs will be followed as described in Section 11.4.11.

The primary reason for discontinuation/early withdrawal must be specified in the eCRF and final IP accountability must be performed.

9.8.3 *Subject replacement*

Subjects who are prematurely withdrawn from the study may be replaced at the Sponsor’s discretion after consultation with the Investigator.

9.9 Randomization

On Visit 2, the subjects will be randomized to a treatment sequence consisting of the nine IP doses, see Table 9-1. The randomized treatment sequence at Visit 2 and 3 will start with either of treatment A or treatment B (to facilitate abstinence for the primary objective, see Section 8.1). A computer-generated randomization list will be created using SAS Proc Plan, SAS Version 9.4. The randomization list will contain subject number, treatment sequence, period, and treatment. As this is an open study, the treatment sequence to which each subject is allocated will be recorded in the eCRF.

The randomization list will be generated by CTC or delegate and provided to the packing company. The original randomization list will be kept by the randomizer. A copy of the randomization list will be provided to the clinic.

Table 9-1 *IP treatments and type of extraction*

Label	Treatment (type of extraction)
A	ZYN Moist Wintergreen (1) (nicotine extraction)*
B	ZYN Moist Smooth (nicotine extraction)
C	ZYN Moist Wintergreen (1) (flavor extraction)*
D	ZYN Moist Wintergreen (2) (flavor extraction)*
E	ZYN Moist Chill (flavor and nicotine extraction)
F	ZYN Moist Cool Mint (flavor extraction)*
G	ZYN Moist Citrus (flavor and nicotine extraction)
H	ZYN Moist Spearmint (flavor and nicotine extraction)
I	ZYN Moist Deep Freeze (flavor and nicotine extraction)

*Combined analysis of nicotine and flavor compound is not possible

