6.2 Study rationale

The overarching aim of the study is to evaluate if the different flavor components have an impact on the nicotine extraction from a ZYN Moist 9 mg product compared to an unflavored ZYN Moist 9 mg product. In addition, the extraction of selected flavor components will be determined.

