6.3 Risk/benefit assessment

It may be considered problematic to expose research subjects to a novel nicotine delivery product with properties of which are not yet fully known. However, all research subjects are required to be daily users of oral tobacco/nicotine products since at least one year (with an average or above snus consumption) so the participants are well acquainted with, and used to, the effects of nicotine.

Aside from the nicotine, all ingredients used in the test products are food-approved (similar to ingredients in conventional snus). ZYN Moist is commercially available on the Swedish market. The nicotine in ZYN Moist is of pharmaceutical grade, same as the nicotine in nicotine replacement products (gum, lozenges, mouth spray etc).

So far, no adverse effects have been reported associated with the use of ZYN products apart from mild effects likely to be related to the nicotine exposure (such as salivation, nausea, and dyspepsia).

Pregnant and breastfeeding women or individuals with a history of hypertension or any cardiovascular disease, who may be particularly vulnerable to nicotine exposure, are excluded from participation.

The potential adverse effects of the study procedures are likely to be minor and/or clinically insignificant, and are from a research ethics perspective, counterbalanced by the potential positive effects of the novel nicotine pouch as a reduced toxicity alternative to conventional oral tobacco. The evidence on the health effects of nicotine exposure is based on existing tobacco products.

All subjects are required to provide informed consent prior to any study procedures.

Risk assessment with regards to the COVID-19 pandemic:

Current recommendations from the authorities will be considered on a day-to-day basis. Ongoing risk evaluation, assessment sessions with Sponsors, Investigators, CRO/vendor representative members to align on local restrictions, impact assessment, contingency plans and study-specific risk mitigation strategies will be made to safeguard the study conduct and the safety of the study subjects. This study is a short-term study including a healthy population. Hence, study participation is not expected to confer increased risks to the study subjects in terms of COVID-19 exposure.

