8 STUDY DESIGN

8.1 Overall study design and schedule of events

This is an open, randomized, nine-way cross-over, single dose administration study designed to assess in vivo extraction of nicotine and/or flavor compounds of non-tobacco-based nicotine pouches. The study will include 36 subjects.

The study will include a screening visit, two treatment visits for administration of in total 9 doses of IP, and a follow-up (FU) telephone visit.

Screening (Visit 1) will take place within 28 days prior to Visit 2 and will include an eligibility check including review of health status and evaluation of nicotine/tobacco use, see Table 8-1 for details.

Subjects shall be abstinent from snus and all other nicotine containing products for at least 12 hours before each treatment visit and are instructed to abstain from snus, cigarettes, or other nicotine delivery products as from 8.00 p.m. the evening before each treatment visit. The subjects should certify abstinence at the beginning of each treatment visit. The two treatment visits start with administration of one IP dose for the primary objective and are performed during the morning hours to facilitate abstinence. The subjects are instructed not to eat, drink, chew chewing gum, use nicotine free pouches or brush teeth from 30 minutes before and during

application of the IP [3]. Following administration of 3 or 4 doses of IP, according to a pre-determined randomized order, with at least 60 minutes between doses (from end of administration to start of administration).

The IPs are administered as single doses and the subject keeps the pouch still between the upper lip and the gum for 60 minutes and are instructed not to manipulate the pouch with the tongue or lips. After 60 minutes the pouches are collected and frozen (-20°C) pending analysis of residual nicotine and flavor compound content.

Table 8-1 Schedule of events

Visit Assessment / Study days	Refer to CSP section:	Screening	Treatment visits		Follow up
		Visit 1 Day -28 to Day 1	Visit 2 Day 1	Visit 3 ≥1 day after Day 1	Visit 4 (Phone call) 5 days (-3/+3) after last dose ¹
Informed Consent	13.3	X			
Inclusion/exclusion criteria	9.4, 9.5	X			
Demographics	11.2	X			
Medical/surgical history	11.2.4	X			
History of nicotine use	11.2.5	X			
Weight/height (BMI)	11.2.6	X			
Physical Examination	11.2.7	X			
Alcohol test ²	11.2.8	X	X		
Urine Drug Screen ²	11.2.9	X	X		
Pregnancy Test ³	11.2.10	X	X		
Randomization	9.9		X		
IP treatment ⁴	10.5		X ⁵	X ⁵	

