Baseline symptoms	11.2.11	X	X ⁶		
Adverse events	11.4				X ⁷
Prior and concomitant medications ⁸	11.2.12				X

BMI = Body mass index, WOCBP = women of childbearing potential

1. Or after early withdrawal.
2. Alcohol and Drug tests may also be performed at additional random occasions during the study.
3. WOCBP only. Urine dipstick.
4. The subject uses the pouch for 60 minutes after which it is collected and frozen.
5. Depending on randomization allocation, 4 or 5 doses are administered with at least 60 minutes between each administration (from end of administration to start of administration).
6. Baseline symptoms will be recorded up until first use of IP.
7. AEs will be recorded from first administration of IP.
8. For definitions of prior and concomitant medications, see Section 11.2.12.

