16.5 Analysis of secondary endpoints

16.5.1 *In vivo extracted amount and fraction of nicotine*

The data needed for the analysis of in vivo extracted amount of nicotine are the individual data of amount of nicotine for unused reference pouches and the amount of nicotine left in the study pouches. The difference between the nicotine content of the reference pouch and the study pouch will be used to calculate the extracted amount. The mean of extracted amount (mg/unit) and fraction (%) of nicotine for each IP pouch, will be calculated. The extracted dose of nicotine will be analyzed using the signed Wilcoxon rank sum test for within subject difference (i.e. between IPs).

Amount and fraction of nicotine in reference pouches and in used pouches will be presented through descriptive statistics.

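### Secondary nicotine comparisons of Chill, Citrus, Spearmint and Deep Freeze with Smooth are confounded with first-slot versus later-slot dosing position

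*Protocol*

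**What the plan says.** **Order of dosing.** Section 9.9: "The randomized treatment sequence at Visit 2 and 3 will start with either of treatment A or treatment B". Section 8.1 agrees and gives the reason: "The two treatment visits start with administration of one IP dose for the primary objective and are performed during the morning hours to facilitate abstinence". It covers the rest of the visit with the phrase "Following administration of 3 or 4 doses of IP, according to a", where the order in question is a randomized one. Footnote 5 of Table 8-1 gives the visit total: "Depending on randomization allocation, 4 or 5 doses are administered with at least 60 minutes between each administration". Section 10.5 provides for one dose of each product. Section 8.1 requires at least 12 hours without nicotine before each visit, but a gap of only 60 minutes or more between doses within a visit.

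**What is measured.** Table 9-1 lists six labels with a nicotine assay: A, B, E, G, H and I. Labels C, D and F are assayed for flavor only.

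**What is compared.** Section 6.2 states the overarching aim, to "evaluate if the different flavor components have an impact on the nicotine extraction" relative to the unflavored product. Table 7-1 makes comparison of nicotine extraction between products a secondary objective. Section 16.5.1 tests it with a "signed Wilcoxon rank sum test for within subject difference (i.e. between IPs". Section 16.1 sets a 5% level for all pairwise tests. Nothing in these sections mentions dosing position.

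**The concern.** A crossover comparison is protected by randomization only if the two products can appear in the same positions. Here Smooth is always the first pouch of a visit and the four other flavored products measured for nicotine never are. Any difference in extraction between a first pouch, taken in the morning after abstinence, and a later pouch, taken after one to four earlier pouches that day, passes in full into the comparison with Smooth.

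The overarching aim is flavored versus unflavored. Of the five flavored products assayed for nicotine, only Wintergreen (1) is compared with Smooth on equal footing. For the other four, a significant result could come from flavor or from position. A null result could also hide a flavor effect that position offsets.

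A position effect is conceivable on the protocol's own account: section 6.3 lists "mild effects likely to be related to the nicotine exposure (such as salivation, nausea, and dyspepsia" among the effects reported with these products, and section 6.1 links saliva production to extraction. Neither section says that extraction changes with slot.

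**Working it through.** **1. The plan's own figure.** Section 16.2 gives CV 31%, 80% power, a 90% confidence interval and limits 0.80 to 1.25. Take the true ratio as 1 (not stated) and the CV as within-subject. On the log scale, σ = √ln(1 + 0.31²) = 0.303, and the SD of a paired log difference is √2 × 0.303 = 0.428. Exact power of the two one-sided tests with n − 1 degrees of freedom is 0.784 at n = 32, 0.801 at n = 33 and 0.844 at n = 36. The stated 33 reproduces and is not in dispute.

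**2. Who can be where.** There are two visits and so two first slots. Each is taken by A or B, and each of A and B is given once.

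| Product | First slot | Slots 2–5 |
|---|---|---|
| A, B | 100% of subjects | 0% |
| E, G, H, I | 0% | 100% of subjects |

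Write τ for a product effect and π for a slot effect. For Chill against Smooth the expected difference is (τ_E − τ_B) + (mean π over slots 2–5 − π_1). For A against B the slot term is π_1 − π_1 = 0. For E against G both products are spread at random over slots 2–5, so no first-slot term enters.

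**3. Can a model separate them?** I built a 36-subject, nine-dose layout that follows sections 8.1 and 9.9 (half the subjects 4 + 5 doses, half 5 + 4; A/B order balanced; the other labels permuted) and checked whether each contrast is estimable.

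| Terms besides subject and product | A − B | E − G | E − B, E − A |
|---|---|---|---|
| Slot, categorical (with or without visit) | yes | yes | no |
| Period 1–9, categorical | yes | yes | yes |
| Period 1–9 plus categorical slot | yes | yes | no |
| Slot, linear | yes | yes | yes |
| Slot, linear, plus a first-slot step | yes | yes | no |

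With categorical slot, G − B, H − B and I − B behave as E − B does. The models that recover the contrasts with Smooth do so only because they leave out a first-slot step.

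**4. Illustration of size.** The protocol gives no position effect, so the effects below are assumptions. Simulate n = 33 pairs with no product difference and test with the signed-rank test at two-sided 5%. With correlation 0 between a subject's two values the SD of the log difference is 0.428. With correlation 0.5 it is √(2 × [ln(1 + 0.31²) − ln(1 + 0.5 × 0.31²)]) = √(2 × [0.0918 − 0.0469]) = 0.299.

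| Assumed position effect | Correlation 0 | Correlation 0.5 |
|---|---|---|
| none | about 5% | about 5% |
| 5% higher | 9% | 14% |
| 10% higher | 21% | 40% |
| 15% higher | 42% | 73% |

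Entries are rejection rates for one product against Smooth. Repeat runs, including runs on the untransformed scale, move them by a few percentage points (for example 68–71% in place of 73%). A 10% lower extraction in later slots gives about 26% and 47%. A 2% effect gives about 5–6%, barely above nominal.

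**The case against.** The strongest reply is that the arrangement is deliberate and openly explained: the first slot protects abstinence for the primary pair, and that contrast is sound. Only secondary comparisons are touched, and section 16.5.1 names no specific pairs. This stands, and it limits the weight of the point. It does not remove it, because section 6.2 and Table 7-1 make flavored-versus-Smooth comparisons part of what the trial sets out to answer.

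The evidence for a mechanism is also thin. Section 6.1 ties saliva to constitutional differences between people, which a within-subject comparison removes. Section 6.3 does not say that salivation persists beyond the gap between doses, and it could arise with the first pouch as well. The endpoint is nicotine left in the pouch, and the conditions of use are the same in every slot. A reader might infer that the comparisons with Smooth are biased. The documents do not support that; they show only that bias cannot be excluded.

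A reader might also infer that no statistical adjustment could help. That is too strong. A steady trend over successive pouches can be estimated from slots 2–5 and projected back to slot 1. Only a separate first-slot step is beyond reach. The signed-rank test takes no covariates, however, so such an adjustment needs a different model.

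Finally, the 5–15% effects are assumed, and the correlation 0.5 column treats the 31% as a total CV, which section 16.2 does not specify.

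**Conclusion.** The point holds as a structural confounding. Sections 8.1, 9.9 and 10.5 together place Smooth and Wintergreen (1) in the first slot in every subject and Chill, Citrus, Spearmint and Deep Freeze in slots 2–5 in every subject, and no section acknowledges or undoes this. Comparisons of those four products with Smooth or with Wintergreen (1) cannot distinguish product from first-slot position without assuming away a first-slot step.

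The size of any bias is unknown. The illustrated error rates (about 9–14%, 21–40% and 42–73% per product) depend on assumed position effects of 5%, 10% and 15%, a CV of 31%, n = 33 and a correlation between 0 and 0.5; with a negligible position effect they fall to the nominal level.

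The primary equivalence test, its sample size and the comparisons among E, G, H and I are not affected by this. A reader might infer that A and B should be moved out of the first slot. The documents do not support that, since it would give up the abstinence that section 8.1 sets out to secure for the primary pair. This is an inexpensive improvement to what the secondary analysis may claim.

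**What to change.** - **Section 16.5.1:** limit confirmatory wording on nicotine to A versus B and to E, G, H and I among themselves. Report A or B versus E, G, H and I as descriptive estimates, labelled as confounded with dosing position.
- **Section 6.2:** qualify the aim so that, for the four products not given first, the comparison with the unflavored product is stated to be descriptive.
- **Optional:** add a mixed-model sensitivity analysis with subject, product and a linear slot term, and state beside it that it assumes no first-slot step. This is an addition to the signed-rank test, since that test cannot carry a slot term.

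The cost is a narrower secondary claim, some changed wording and, if the option is taken, one extra model. No dose, visit or subject is added, and the dosing order stays as it is.

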9.10 Blinding

This is an open-label study, i.e. the Investigator, study staff and subjects will know the type of treatment to be received.

10 TREATMENTS

The IPs are supplied by Swedish Match North Europe.

10.1 Identity of investigational products

ZYN Moist Wintergreen (1)* containing 9 mg nicotine/pouch

ZYN Moist Wintergreen (2)* containing 9 mg nicotine/pouch

ZYN Moist Chill containing 9 mg nicotine/pouch

ZYN Moist Cool Mint containing 9 mg nicotine/pouch

ZYN Moist Citrus containing 9 mg nicotine/pouch

ZYN Moist Spearmint containing 9 mg nicotine/pouch

ZYN Moist Deep Freeze containing 9 mg nicotine/pouch

ZYN Moist Smooth containing 9 mg nicotine/pouch

*ZYN Moist Wintergreen product (1) and (2) contains different amount of the flavor wintergreen

10.2 Manufacturing, packaging and labelling

The IP will be manufactured and packaged in compliance with the Swedish law on food production.

The IP will be transferred from the original container, weighed and individually packaged in identical sealed food approved test containers at the Swedish Match analytical lab.

The containers will be labelled with unique identification numbers by Swedish Match in accordance with the randomization list.

10.3 Conditions for storage

The IP will be stored in an access-controlled storage area at CTC, at refrigerated temperature (4-8°C).

The temperature is recorded continuously by an automatic temperature control system.

10.4 Preparation and accountability

The IP will be dispensed according to the randomization list by the site personnel. Before administration to the subjects, the IP should be placed in room temperature for at least 30 minutes to allow the IP to adapt to room temperature.

The Investigator will maintain a Storage and Accountability Log as well as a Dispensing Log detailing the dates and quantities of IP received, prepared for, and used by each subject and study product returned or destroyed at the end of the study. Any discrepancies between prepared and returned IP must be explained and documented. Products deliberately and/or accidentally destroyed by the site or the subject must be accounted for.

10.5 Treatment administration

A single dose of each IP will be given in accordance with the randomization list. The pouch will be placed between the upper lip and gum, and kept still there for 60 minutes. The subject is instructed to not manipulate the pouch with the tongue.

10.6 Treatment compliance

All IP will be administered at the research clinic under medical supervision to ensure compliance.

10.7 Return and destruction of investigational medicinal products

Any unused study medication and all empty containers will be destructed at the site upon confirmation from the Sponsor. The Monitor will perform final IP accountability reconciliation at the study end to verify that all unused IP is adequately destroyed and documented.

11 STUDY ASSESSMENTS

The study assessments are described in the sections below and the timing of these assessments are detailed in the schedule of events (Table 8-1).

11.1 Recording of data

The Principal Investigator will provide the Sponsor with all data produced during the study from the scheduled study assessments. He ensures the accuracy, completeness, legibility, and timeliness of the data reported to Sponsor in the eCRF and in all required reports.

11.2 Demographics and other baseline characteristics

11.2.1 *Informed consent*

Signed informed consent must be obtained before any screening procedures are initiated. The informed consent procedure is further described in Section 13.3.

11.2.2 *Eligibility criteria*

Eligibility criteria should be checked during screening and verified before randomization/IP administration. The criteria are specified in Sections 9.4 and 9.5.

11.2.3 *Demographic information*

The following demographic data will be recorded: gender, age, ethnicity and race.

11.2.4 *Medical/surgical history*

Medical/surgical history will be obtained by subject interview in order to verify that the eligibility criteria are met.

11.2.5 *History of nicotine use*

History of snus or oral nicotine product use in terms of brand of product, average consumption per day (last month), and duration of use (years) as well as history of smoking in terms of number of cigarettes per day (the last month) will be obtained by subject interview.

11.2.6 *Weight and height*

Weight and height will be measured without shoes. BMI will be calculated, with one decimal, from the height and weight recorded.

11.2.7 *Physical examination*

A brief physical examination will include assessments of lungs, cardiovascular, abdomen (liver and spleen), and extremities.

Any abnormalities will be specified and documented as clinically significant (CS) or not clinically significant (NCS).

11.2.8 *Alcohol test*

An alcohol test will be performed at time points outlined in the schedule of events (Table 8-1). Additional random tests can be performed during the study period.

11.2.9 *Urine drug screen*

Urine will be screened for drugs of abuse at time points outlined in the schedule of events (Table 8-1) using the Alere™ Drug Screen Test Panel. Additional random tests can be performed during the study period.

11.2.10 *Pregnancy test*

All females of childbearing potential will do a pregnancy test (urine dipstick) at time points outlined in the schedule of events (Table 8-1).

11.2.11 *Baseline symptoms*

A baseline symptom is defined as an event that occurs between the subject's signing of the ICF until the first administration of IP (i.e. an event that occurs during the screening period). Such events are not AEs and will be recorded as baseline symptoms in the Medical History Log in the eCRF.

11.2.12 *Prior and concomitant medication*

Prior and concomitant medications taken within 2 weeks prior to screening will be obtained by subject interview in order for documentation of the subject's status regarding current medications (see also Section 9.6.2).

Medications are classified as prior if the stop date was before or on the day of the first dose administration (pre-dose) and as concomitant if ongoing on the day of the first dose administration, stopped after the first dose administration or started after the first dose administration. To distinguish between prior and concomitant medications on Visit 1 (i.e. the first dosing day), the start time of any newly introduced medication or the stop time of any previously ongoing medication must be recorded in the eCRF.

Any use of concomitant medication from screening until the last end-of-study visit must be documented appropriately in the subject's eCRF. Relevant information (i.e. name of medication, dose, dose form, unit, route, frequency, start and stop dates, reason for use) must be recorded. All changes in medication should be noted in the eCRF.

